### Appendix 1 Activities of schizophrenia education and contact intervention

Time	Intervention group activities		Control group activities
Week 1 -Week 4	
investigative learning: nursing students to access information through evidence-based research to discover the information themselves. A guide outline will be used to help nursing students to search information, and this outline may add some more guidance when stage one is done. Nursing students will be asked relevant information during week one, and every two points will require one hour. Students will be asked to spend two hours every two days to search relevant information of schizophrenia.
 
Collaborative learning activities Higher-order thinking activities interactive learning activities (Week 1-Week 4)
	
Week one: 1) Traditional Chinese culture and religion toward mental illness or schizophrenia. 2) Reasons of schizophrenia stigma formation. 3) Diagnosis and treatment of schizophrenia. 4) Violent, aggressiveness, and independence about schizophrenia. 5) How to communicate with people who have schizophrenia. 6) Daily stigma toward schizophrenia from media, like newspapers, TV series, movies, news, advertisement. 7) The early warning signs of schizophrenia and how to provide initial help to someone in a schizophrenia crisis and the symptoms, causes, and evidence-based treatments for schizophrenia. Summary: Knowledge and information sharing among students
 
Week two: Nursing students interview people who recover from schizophrenia share their experiences throughout the treatment and recovery period and discuss problems with them (a female and a male). Summary: Knowledge and information sharing among students
 
Week three: Scenario-based simulation, in the simulation application, students took the roles of the persons with schizophrenia or the nurses, and evaluate their performance, and view the events from a different perspective. Summary: Knowledge and information sharing among students
 
Week four: Nursing students' self-criticism after scenario-based simulation, nursing students will be asked to write their opinion about schizophrenia and People with Schizophrenia. After that, nursing students were read their opinions and discussed their assumptions. Self-reflection, critical reflection, and imaginative activities enabled them to examine themselves critically (Theme: What would I feel if I have schizophrenia). Nursing students prepared concept maps for the problems and solutions of a person with schizophrenia in the daily life.
	
Giving a book about schizophrenia to nursing students in the control group and asking them to finish reading it in a month.


---

### Appendix 2 Questioning route in the focus groups before pilot study

1	What do you know about Schizophrenia (SZ)? (Probe: causal factors, manifestation, prognosis; where you obtained such information?)
2	What do you think the life of people with SZ? (Probe: social support> intimate relationship > education> working)
3	What's your experiences of interacting with people with SZ and/or their family members, (if no personal encounter, any story you heard?) [When> what happened> who> what did you say> How do you feel>].
4	What do you think of traditional Chinese culture and religion on schizophrenia? [How do Confucianism, Taoism, and Buddhism view and deal with schizophrenia> What do these religions think the reason of schizophrenia and how to deal with it]
5	What do you think of the pressure experienced by people with SZ compared with other mental illnesses?
6	How do you think the stigma often encountered by people with SZ?
7	What do you think of caring people with SZ in the future?

---

### Appendix 3 Basic socio-demographic Information

---

Age

Gender

Male

Female

Ethnic groups (Please fill in your nationality, such as Han, Miao, etc.)

Marital status

Married

unmarried

Name of university (University name)

Name of province

Grade

Year 4

Year 5

---

Religion (Religion of belief such as Buddhism, Taoism, if not, fill in none)

Average families income per year (Ten thousand yuan)

Friends or family members with mental illness problem	Yes	No
-------------------------------------------------------	-----	----

Have you been in contact with a People with Schizophrenia in the past	Yes	No
-----------------------------------------------------------------------	-----	----

Did you suffer from mental illness?	Yes	No
-------------------------------------	-----	----

---

Have you participated in similar  
research before

Yes

No

---

#### **Appendix 4 Knowledge about Schizophrenia Test (KAST)**

##### **1. Schizophrenia is most likely caused by:**

- A. Brain problem
- B. Drug use
- C. Evil spirits
- D. Pollution
- E. Stress

---

**2. A common symptom of schizophrenia is:**

- A. Being overly happy and having extra energy
- B. Overeating and weight gain
- C. Sudden anxiety attacks
- D. Thinking that others are watching or following
- E. Violence, theft, or physical attacks toward others

**3. The best person to decide if someone has schizophrenia is a(n):**

- A. Emergency room doctor
- B. Family member
- C. Preacher or Minister
- D. Psychiatrist
- E. School teacher

---

**4. With treatment, the most common long-term outcome**

**for schizophrenia is:**

- A. Complete cure
- B. Dementia
- C. Mild to moderate mental retardation
- D. Relief of symptoms, with possibility of relapse
- E. Severe mental deterioration

**5. Medicines that are used for hearing voices are called:**

- A. Antibiotics
- B. Anti-depressants
- C. Anti-psychotic

---

D. Sedatives

E. Tranquilizers

**6. The best place to get information about schizophrenia is from:**

A. Books or websites

B. Friends

C. Neighbors

D. Newspapers

E. Preachers or ministers

**7. To help deal with stress, most patients with schizophrenia benefit from:**

A. Alcohol use

B. Counseling or psychotherapy

C. Cutting back on social activities

---

D. Pain-relief medications

E. Physical therapy

**8. The cause of schizophrenia is most likely related to:**

A. Biology

B. Environment

C. Family

D. Personality

E. Society

**9. A person strongly believes that the FBI has put a computer chip in his/her body. This symptom is called a:**

A. Daydream

B. Delusion

---

C. Hallucination

D. Phobia

E. Worry

**10. A doctor usually makes a diagnosis of schizophrenia by a(n):**

A. Blood test

B. CAT scan

C. Interview

D. Reading test

E. Urine test

**11. Most people who have schizophrenia need to be in some sort of treatment for:**

A. Days

B. Weeks

---

C. Months

D. Years

E. Not at all

**12. The best treatment for the symptoms of schizophrenia is:**

A. Medicine

B. Operation

C. Relaxation

D. Strict diet

E. Vitamins

**13. People with Schizophrenia benefit most from:**

A. Being put into a hospital for years

- 
- B. Having fun or exercising
  - C. Strict schedules with full-time employment
  - D. Support from family/friends and low stress
  - E. Vitamins, minerals, or herbs

**14. A 19-year-old begins to hear voices and act paranoid several months after graduating from high school. The most likely causes of his symptoms is:**

- A. Drinking alcohol
- B. Genetic tendency toward developing an illness
- C. Graduating high school
- D. Personality weakness
- E. Puberty and adolescence

---

**15. The symptoms of schizophrenia usually begin in which stage of life?**

- A. As a baby
- B. Elementary school years
- C. Late teen-age years or young adulthood
- D. 40–50 years old
- E. 60–70 years old

**16. Which of the following is one of the new “atypical” medicines for schizophrenia?**

- A. Chlorpromazine (Thorazine)
- B. Haloperidol (Haldol)
- C. Fluphenazine (Prolixin)
- D. Trifluoperazine (Stelazine)
- E. Quetiapine (Seroquel)

---

**17. Which group is the best source of information and support for family members of People with Schizophrenia?**

- A. American Medical Association (AMA)
- B. Association of Psychologists and Psychiatrists (APAP)
- C. Centers for Disease Control and Prevention (CDC)
- D. National Alliance for the Mentally Ill (NAMI)
- E. Schizophrenia Family Association (SFA)

**18. After hospitalization, a patient with schizophrenia would benefit most from:**

- A. Constant observation by family
- B. Eating more meats and breads
- C. Follow-up with a preacher or minister
- D. Follow-up with an outpatient psychiatrist

## Appendix 6 Reported and Intended Behaviour Scale (RIBS)

**Instructions:** The following questions ask about your experiences and views in relation to people who have mental health problems (for example, people seen by healthcare staff), For each of questions 1-4, please respond by taking one box only.

	Yes	No	Don't know
1. Are you currently living with, or have you ever lived with, someone with a mental health problem?			
2. Are you currently working with, or have you ever worked with, someone with a mental health problem?			
3. Do you currently have, or have you ever had, a neighbor with a mental health problem?			
4. Do you currently have, or have you ever had, a close friend with a mental health problem?			

**Instructions:** For each of the questions 5-8, please respond by ticking one box only.

	Agree strongly	Agree slightly	Neither agree nor disagree	Disagree slightly	Disagree strongly	Don't know
5. In the future, I would be willing to live with someone with a mental health problem						
6. In the future, I would be willing to work with someone with a mental health problem						
7. In the future, I would be willing to live nearby to someone with a mental health problem						
8. . In the future, I would be willing to continue a relationship with a friend who developed a mental health problem						

Thank you very much for your help

14	I believe that emotion has no place in the treatment of medical illness.								
15	Empathy is a therapeutic skill without which success in treatment is limited.								
16	An important component of the relationship with my patients is my understanding of their emotional status, as well as that of their families.								
17	I try to think like my patients in order to render better care.								
18	I do not allow myself to be influenced by strong personal bonds between my patients and their family members.								
19	I do not enjoy reading non-medical literature or the arts.								
20	I believe that empathy is an important therapeutic factor in medical or surgical treatment.								

**Jefferson Scale of Physician Empathy**

**Scoring Algorithm**

A respondent must answer at least 16 (80%) of the 20 items; otherwise, the form should be regarded as incomplete and excluded from the data analysis.

In the case of a respondent with 4 or fewer unanswered items, missing values should be replaced with the mean score calculated from items completed by the respondent.

To score the scale, items 1, 3, 6, 7, 8, 11, 12, 14, 18, and 19 are reverse scored items (i.e., Strongly Agree=1,...Strongly Disagree=7), while the other items are directly scored on their Likert weights (i.e., Strongly Agree=7,...Strongly Disagree=1).

The total score is the sum of all item scores.

The higher the score, the more empathic the behavioral orientation.

### Appendix 8 Fidelity checklist

Treatment fidelity strategies	present	absent but should be present	not applicable
Treatment design			
1. Provided information about treatment dose in the intervention condition			
Length of contact session(s)			
Number of contacts			
Content of treatment			
Duration of contact over time			
2. Provided information about treatment dose in the comparison condition			
Length of contact session(s)			
Number of contacts			
Content of treatment			
Duration of contact over time			
3. Mention of provider credentials			
4. Mention of a theoretical model or clinical guidelines on which the intervention is based			
Training providers			
1. Description of how providers were trained			
2. Standardized provider training			
3. Measured provider skill acquisition post-training			
4. Described how provider skills maintained over time			
Delivery of treatment			
1. Included method to ensure that the content of the intervention was being delivered			

as specified (e.g., treatment manual, checklist, computer program)			
2 . Included method to ensure that the dose of the intervention was being delivered as specified (e.g., records number of contact minutes.			
3. Included mechanism to assess if the provider actually adhered to the intervention plan (applies to human providers only?) (e.g., audiotape, observation, self-report of provider, exit interview with participant)			
4. Assessed nonspecific treatment effects			
5. Used treatment manual			
Receipt of treatment			
1. Assessed subject comprehension of the intervention during the intervention period			
2. Included a strategy to improve subject comprehension of the intervention above and beyond what is included in the intervention			
3. Assessed subject's ability to perform the intervention skills during the intervention period			
4. Included a strategy to improve subject performance of intervention skills during the intervention period			
Enactment of treatment skills			
1. Assessed subject performance of the intervention skills assessed in settings in which the intervention might be applied			
2. Assessed strategy to improve subject performance of the intervention skills in settings in which the intervention might be applied			

### Appendix 9 Questioning route used in the focus groups

1	How do you evaluate the program? (The investigative learning, high-order thinking, and collaborative learning activities) [Which part do you like the most or which part you dislike the most, and why? ]
2	How do you comment on the ease of finish of the intervention? (The cost of time). Why do you think it is easy or difficult to adherence? >What do you think of the frequency of intervention and the duration of each intervention? >How often do you think is the best frequency and how long do you think is the best duration of intervention? ]
3	What do you think of online intervention? [What do you think of the effects of online intervention of these three interventions (investigative learning, higher-order thinking, and collaborative learning activities), and why?]
3	How would you evaluate the questionnaires that you completed in the study? [Are these questionnaires suitable for measuring schizophrenia knowledge, attitudes, behavior, empathy, and stigmatization intention behavior? Why? ]
4	Please describe how this intervention affects the ways you think of SZ.
5	What are your suggestions to improve the study design?
6	Is there anything else related to the study that has not been discussed?

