## **Chinese Culture-Specific Intervention to Decrease the Stigma of Nursing Students towards Schizophrenia—A Pilot Randomized Controlled Trial**

### **Introduction**

Mental illness stigma does enormous damage to those with mental illness as well as their families, and the health care system (Brouwers, 2020). Schizophrenia is the most stigmatized disease among mental illnesses (Valery & Prouteau, 2020). In China, nearly 7.8 million people are diagnosed with schizophrenia, and 100,000 new diagnoses are recorded each year (Hu, 2018; Yao et al., 2013). The stigma of schizophrenia is mainly characterized by the stereotypes of danger, unpredictability, and a poor prognosis (Crisp, Gelder, Rix, Meltzer, & Rowlands, 2000). People with schizophrenia are widely considered as more dangerous and unpredictable than people with other mental illnesses (Reavley & Jorm, 2014).

In different cultures, people have different understandings of stigma meanings, treat it in different ways and yield different results (Yang, 2007). In China, some people believe that schizophrenia is caused by black magic or possessed or disturbed by spirits (gods or devils) (Tseng et al., 2013). Studies showed that socio-cultural and religious factors strongly affect stigmatizing attitudes (Waqas et al., 2020).

However, in China, few studies have been conducted with a focus on Chinese culture when it comes to decreasing mental illness stigma. China is a developing country with a culture of face-saving and Confucianism, totally different from western countries (Yang et al., 2014). Nurses play an essential role in all health care systems. When nursing students begin their nursing career, their attitude and behavior toward schizophrenia will affect the treatment and nursing of people with schizophrenia. A study showed that compared with medical students, nursing students hold even a more negative attitude towards people with schizophrenia (Taşkın et al., 2003).

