### **Phase 3: Process evaluation**

This phase aims to collect feedbacks from online focus group interview to explore the barriers and facilitating factors in implementing the intervention, figure out additional problems which may affect the intervention, and refine the study design for a future full power RCT.

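### Item 4 of the post-programme focus-group guide presupposes an effect on students' views, and no item expressly asks about no change, less favourable views or distress

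*Protocol*

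**What the plan says.** The Protocol's section on Phase 3 (Process evaluation) sets out to find barriers and facilitators, to "figure out additional problems which may affect the intervention", and to refine the design of a later full-size trial. Appendix 9 gives the questions. It is not labelled Phase 3, but it asks about a completed programme, whereas Appendix 2 is expressly the guide for use before the pilot. Reading Appendix 9 as the Phase 3 guide is therefore reasonable.

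The only entry about what students now think of schizophrenia is item 4: "Please describe how this intervention affects the ways you think of SZ".

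Two neighbouring items are built differently. Item 1 asks "Which part do you like the most or which part you dislike the most, and why", and item 2 asks "Why do you think it is easy or difficult to adherence".

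On content, the Introduction states: "The stigma of schizophrenia is mainly characterized by the stereotypes of danger, unpredictability, and a poor prognosis". Appendix 1 lists among the week-one search topics "Violent, aggressiveness, and independence about schizophrenia". Later weeks add role-play as a person with schizophrenia or as a nurse, self-criticism after the simulation, and reflection on how one would feel with the illness.

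**The concern.** A question that asks how something affected you takes for granted that it did. A student whose views did not move has to reject the premise before answering. A student who came away more wary can answer truthfully, but must volunteer an unwelcome reply without being asked for it. The setting makes this harder: the study is open-label, the students know what the programme is for, the groups start with four peers, and the discussions are videotaped.

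What is at stake is the use of Phase 3 for refining the programme. Some activities touch the danger stereotype that the Introduction names or are emotionally demanding. The exclusion criteria remove students now under treatment and those in frequent contact with an affected person. Students with a past illness or an affected relative can still enrol, and Appendix 3 asks about both. It is therefore foreseeable that an activity could leave a student unmoved, more worried or upset, and the guide does not ask for that directly.

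**Working it through.** The Protocol states no figure on this point, and no sample size, power or error rate enters. The check is a reading of every entry in Appendix 9 for presupposition, balance and room for a negative reply, followed by a comparison with the other planned data.

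**1. The entries.** They are numbered 1, 2, 3, 3, 4, 5, 6, which makes seven.

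| Entry | Subject | Form | Room for a negative reply |
|---|---|---|---|
| 1 | Evaluation of the programme | Two-sided, with probe | Yes, asks for dislikes |
| 2 | Time cost and adherence | Two-sided, with probes | Yes, asks for difficulty |
| 3 (first) | Online delivery and effects of the components | Open opinion, with probe asking why | Neutral; little or no effect is a possible reply |
| 3 (second) | Suitability of the questionnaires | Open, with probe | Yes |
| 4 | Effect on views of schizophrenia | Presupposes an effect, no direction, no probe | Only if volunteered |
| 5 | Suggestions for the design | Open | Yes |
| 6 | Anything not yet discussed | Open | Yes |

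**2. The counts.**
- Entries that presuppose an effect on views: 1 of 7 (item 4).
- Entries that expressly ask about no change, worsening or distress: 0 of 7.
- Entries that invite or allow criticism of the programme or study: 5 of 7 (items 1, 2, second 3, 5 and 6).
- Neutral opinion on effects: 1 of 7 (first 3).
- Check: 1 + 5 + 1 = 7.

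**3. Is item 4 out of line with the rest of the Protocol?** Yes, mildly. Items 1 and 2 offer both sides. The Phase 1 guide in Appendix 2 also provides for the null case in its question 3, which gives an alternative to students who have never met an affected person. Item 4 provides for neither.

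**4. Do the Phase 2 data cover the gap?** Only in part.
- The scales are taken at baseline, after the intervention and at three months, against a control group. They can show a group-level worsening. Items 2 and 5 of the attitude scale in Appendix 5 concern recovery and danger, which are close to the stereotypes named in the Introduction.
- The attitude and behaviour scales are worded for mental illness in general. The schizophrenia-specific scale is a knowledge test.
- The first post-baseline measurement follows the whole four-week programme, so the scores cannot show which activity moved views.
- No listed outcome measures distress. The primary outcomes are recruitment time and rate, eligibility, scale response and drop-out. The efficacy scales cover knowledge, attitude, intended behaviour and empathy.

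So two things are left to Phase 3: which activity shifted views and in which direction, and whether any activity was upsetting. The guide leaves the first to a presupposing question and the second to general openings.

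**The case against.** The strongest reply is that one prompt among seven does little harm. Item 4 fixes no direction, so an answer that the programme made someone more wary is a complete answer. Item 1 asks outright for the most disliked part and the reason. The first item 3 asks "What do you think of the effects of online intervention of these three interventions", which is neutral and leaves room for a reply of little or none. Item 5 asks "What are your suggestions to improve the study design". The Data Collection section adds open-ended questioning, a trial of the guide on one participant, and field notes on non-verbal expression and emotional status. In week four students also write down and discuss their opinions, and the sessions are videotaped.

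Most of this stands, and it limits the point. A reader might infer that the process evaluation as a whole is steered to favourable accounts. The documents do not support that: six of the seven entries are balanced, open or neutral, and Phase 3 is expressly aimed at problems. A reader might also infer that a harmful activity would pass unnoticed, or that the interviews would be used to support efficacy. Neither follows. The scales can register worsening, and the Protocol assesses efficacy through those scales and generalized estimating equations, not through the focus groups.

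What the reply does not remove is the presupposition itself and the missing prompt. A student may like an activity and still leave more fearful, so asking about dislikes is not the same question. A closing invitation to add anything else depends on a student raising an awkward answer unasked. Trying the guide on one person does not test it for leading wording.

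**Conclusion.** The point holds as a minor one, confined to item 4 and to the lack of a prompt for no change, less favourable views or distress. Its size is one presupposing question of seven and no express question on the unfavourable outcomes. It does not touch the primary feasibility and acceptability outcomes or any quantitative analysis.

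Two assumptions are involved. The first is that Appendix 9 is the Phase 3 guide, which its content supports. The second is that interviewers keep to the printed wording; one who adds neutral follow-up questions would reduce the problem. That the material on violence hardens views, or that the role-play and self-criticism distress students, is a possibility to be asked about, not something the Protocol shows. The same week-one list also covers how stigma forms and how the media convey it. The right label is a cheap improvement.

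**What to change.** 1. Replace item 4 with a neutral question, for example: *Has taking part changed the way you think of people with SZ, or not? If so, in which direction, and which activity did that? If not, why not?*
2. Add one probe: *Was any part upsetting, or did any part make you more worried about people with SZ?*
3. State under Qualitative Content Analysis that no-change and negative accounts are coded and reported as their own category.

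The cost is one reworded question, one added probe and one coding category. It takes a few minutes within an interview of about 60 minutes, with no extra staff or sessions.
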